## 2.4.2 Secondary endpoints

Patient-reported outcomes are obtained from the bowel habit diary. Each patient fills out the diary every day for one week at baseline, for one week starting at each day of the two interventions

and for one week at the follow-up at week 26. Bivariate comparions are made, comparing differences between FMT and placebo at a) Baseline vs first intervention, b) Baseline vs second intervention, c) Baseline vs longterm follow-up (week 26) for the following variables:

- 1. Median stool consistency (Bristol scale)
- 2. Number of passages of hard stools (BS 1-2)
- 3. Number of passages of liquid stools (BS 6-7)
- 4. Median number of bowel openings per 24 hours
- 5. Number of nightly bowel openings (from bedtime until morning)
- 6. Number of episodes with involuntary defaecation
- 7. Glycemic control measured by patient reported use of insulin (IE)

Patient-reported measures from the schedule of side effects and telephone call 1 week after each intervention

- 8. Mild adverse events (grade 1) following FMT or placebo assessed by CTCAE v5.0
- 9. Adverse events in week 5-8
- 10. Serious adverse events during longterm follow-up

Patient-reported outcomes from questionnaires completed at baseline and 4 weeks after each intervention period and at 26 weeks follow-up. Bivariate comparisons baseline vs week 4, baseline vs week 8, baseline vs week 26:

- 11. Change in Gastrointestinal syndrome rating scale irritable bowel version questionnaire (GSRS-IBS)
- 12. Change in patient assessment of upper gastrointestinal symptom severity index (PAGI-SYM)
- 13. Change in irritable bowel syndrome impact scale (IBS-IS)

Objective measures from the wireless motility capsule performed at baseline and 4 weeks after each intervention period:

- 14. Transit time through the small intestine
- 15. Colonic transit time
- 16. pH drop from the small intestine to the colon

Objective measures from the low-dose CT scan performed at baseline and 4 weeks after the first intervention period:

- 17. Volume of the a) small intestine and b) the colon
- 18. Volume of gas in a) the small intestine and b) the colon

Objective measures from the breath test performed at baseline and 4 weeks after the first intervention period:

19. Rise in hydrogen PPM measured in breath test for small intestinal bacterial overgrowth

Microbiota analysis on faecal samples collected at baseline and 4 weeks after each intervention period:

20. Alpha-diversity of faecal microbiota, 16S

21. Dysbiosis index

Blood samples. Comparisons are made, comparing differences between FMT and placebo at a)Baseline vs first intervention, b) Baseline vs second intervention,22. Glycemic control measured by HbA1C levels

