## 2.3.2 Secondary H0

2. Oral intake of FMT changes the microbiota of the colon and the effect lasts for at least 4 weeks.

3. Oral intake of FMT is superior to placebo in reducing gastrointestinal symptoms in patients with DM1.

4. The effect of two doses of oral intake of FMT (separated by 4 weeks) is superior to one dose.

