## 3.5 Randomisation

Randomisation will determine which group of patients will receive active treatment with FMT and which group will receive placebo capsules. Both participants and investigators will be blinded to the intervention.

Randomisation is performed by the project nurse at the Clinical Trial Unit at the department of Hepatology and Gastroenterology, AUH. The delivery is handled by the CEFTA laboratory staff after contact with the clinical staff. The randomisation list is established by the Clinical Trial Unit, Hepatology and Gastroenterology, AUH. Envelopes with procession information are packed according to the randomisation list. The CEFTA laboratory is continuously packing treatment boxes for each patient at randomisation according to the treatment with FMT + FMT or Placebo + FMT. The packaging of the boxes is standardised with double control and documented as a standard FMT for traceability as in routine FMT. The labeling on the packages does not reveal whether it contains placebo or FMT. Treatment boxes are marked with a number corresponding to the number drawn from the randomisation list, and at the start of the treatment it is ensured that these matches. The randomisation list is kept secret in the projects Trial Master File.

Premature unblinding is possible if investigators deem it necessary or in the event of conditions leading to interruption of the entire trial. This could be following several adverse events (AE) suspected to be in relation to active treatment with FMT, or if the trial terminates prematurely because of inability to include 20 patients. Any unblinding will follow the SOP "Kodebrud" and will be documented in the TMF.

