# 4.0 Statistical considerations

## 4.1 Sample size

This is the first study with FMT to patients with DM1 and therefore the assumptions for formal power calculations are not present. We expect that a group of n = 20 patients with DM1 is sufficient to determine whether there are any serious side effects associated to administration of FMT.

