## 4.2 Statistical analyses

Descriptive statistics such as safety profile/adverse events and demographic data will be reported as the interquartile range (median  $\pm$ IQR). Data from the WMC, Low-dose CT and breath test will be analysed using repeated measures regression with the intervention (FMT or placebo) as random effect.

The final statistical analysis plan, providing details of the analysis and presentation of results, will be finalised before initiation of any statistical analysis. Patients considered for the evaluation of safety and efficacy will be defined in the statistical analysis plan. Statistical analysis will be performed only after unblinding.

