# 5.1 Inclusion criteria

- Adult ( $\geq$  18 years old), male or female patients with DM1 for at least 5 years and
- Average of or above 40 points in the questionnaire: Gastrointestinal syndrome rating scale irritable bowel syndrome version (GSRS-IBS).

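### Questionnaire and diary endpoints are set for unadjusted bivariate comparisons of change, and the questionnaire sentence names no arm contrast although hypothesis 3 is superiority to placebo

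*Protocol*

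**What the plan says.** Hypothesis 3 (protocol section 2.3.2) is a between-arm statement: "Oral intake of FMT is superior to placebo in reducing gastrointestinal symptoms in patients with DM1". It names no endpoint or time point.

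Section 2.4.2 describes the comparisons differently for different groups of endpoints:

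- Diary (7 variables, 3 time contrasts): "Bivariate comparions are made, comparing differences between FMT and placebo at a) Baseline vs first intervention", followed by the second intervention and week 26.
- Questionnaires (GSRS-IBS, PAGI-SYM, IBS-IS): "Bivariate comparisons baseline vs week 4, baseline vs week 8, baseline vs week 26". No arm is mentioned.
- HbA1c: "Comparisons are made, comparing differences between FMT and placebo at a)Baseline vs first intervention, b) Baseline vs second intervention".

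Section 4.2 treats another group separately: "Data from the WMC, Low-dose CT and breath test will be analysed using repeated measures regression with the intervention (FMT or placebo) as random effect". It gives no method for the diary or the questionnaires and leaves details to a statistical analysis plan.

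Patients enter on the main symptom scale itself: "Average of or above 40 points in the questionnaire" (section 5.1, GSRS-IBS). Treatment boxes are packed "according to the treatment with FMT + FMT or Placebo + FMT" (section 3.5), so both arms receive FMT from the second intervention on. On size, section 4.1 plans 20 patients and states that "therefore the assumptions for formal power calculations are not present".

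**The concern.** The three questionnaires are the validated symptom and symptom-impact scales, and hypothesis 3 asks whether FMT beats placebo on symptoms. A comparison of follow-up with baseline does not ask that question. In patients chosen for high scores and given capsules in a blinded trial, scores can fall in both arms with no effect of FMT.

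The protocol summary says the results should supply what is needed to design a powered trial. If a fall from baseline were carried forward as the treatment effect, placebo response and regression to the mean would enter the next sample size calculation.

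The second issue is efficiency. A bivariate comparison of change leaves out the baseline value as a covariate. With about 10 patients per arm, precision that costs no extra data is worth taking.

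**Working it through.** The plan gives no power, alpha, SD or effect size, so there is no figure of its own to reproduce.

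**Inputs from the protocol.** n = 20. The study diagram shows 10 patients per arm; the text states no ratio, so 10:10 is assumed. The GSRS-IBS entry threshold is 40.

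**Assumptions.** Two-sided 0.05, normal data, equal SD at baseline and follow-up, r from 0.5 to 0.8, and an effect of 1 SD for power.

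**1. Number of contrasts.** Diary 7 × 3 = 21 and questionnaires 3 × 3 = 9, so 30 are labelled bivariate. The other listed contrasts are wireless motility capsule 6, CT 4, breath test 1, microbiota 4 and HbA1c 2, which is 17. The total is 47.

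**2. Which contrasts compare FMT with placebo.** Only those in the first period. At weeks 8 and 26 the arms are FMT + FMT and placebo + FMT, so a between-arm difference there compares two doses with one, which is hypothesis 4.

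**3. The literal, within-arm reading.** This was simulated with no treatment effect, a paired test in one arm of 10, and selection on the baseline score itself:

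| Scenario | r = 0.5 | r = 0.7 |
|---|---|---|
| No entry cut-off | about 5% | about 5% |
| Cut-off at the population mean | 23–24% | about 15% |
| Cut-off 0.5 SD above the mean | 42% | 26% |
| Cut-off at the mean plus 0.5 SD placebo response | 78% | 80–81% |

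These are the shares of trials in which the within-arm test is significant. In every scenario the between-arm test stays at about 5%, whether on change or baseline-adjusted.

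In points, the regression to the mean is (1 − r) × SD × 0.798 with the cut-off at the mean. With SD 10 and r = 0.8 it is 0.2 × 10 × 0.798 = 1.6. With SD 12 and r = 0.6 it is 0.4 × 12 × 0.798 = 3.8. The SDs are assumed. Both the table rows with a cut-off and these points are upper cases: Table 1 checks eligibility at visit 1 but first schedules GSRS-IBS at visit 2. If visit 2 is a separate measurement, some or all of the regression happens before baseline.

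**4. The between-arm reading.** Variance of change is 2(1 − r)σ². Baseline-adjusted variance is (1 − r²)σ². The ratio is (1 − r²) / [2(1 − r)] = (1 + r)/2. Estimating the slope from 20 patients multiplies this by about 17/16:

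| r | (1 + r)/2 | × 17/16 | Power, change | Power, adjusted |
|---|---|---|---|---|
| 0.5 | 0.75 | 0.80 | about 56% | about 66% |
| 0.7 | 0.85 | 0.90 | about 78% | about 82% |
| 0.8 | 0.90 | 0.96 | about 92% | about 93% |

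Power is for a 1 SD effect with 10 per arm. The adjusted figures are simulated with the slope estimated. Ignoring the slope cost would give 69% and 84% at r = 0.5 and 0.7, which is too favourable.

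**The case against.** The strongest reply is that the questionnaire sentence is shorthand. It stands in the same list as the diary sentence, uses the same word for the comparison, pairs time points in the same way, and calls each endpoint a change. Section 3.1 says the design serves to evaluate whether FMT is superior to placebo. This reading is plausible, so the sentence is unclear rather than certainly within-arm. It remains a defect, because the diary and HbA1c sentences name the arms and this one does not.

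It can also be said that change scores and baseline adjustment are both valid in a randomised comparison and that analysis details go to the analysis plan. Both hold about 5% type I error, so the adjustment point concerns efficiency, not validity. But a bivariate comparison is a stated method, and a better one is available on the same data.

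Two stronger readings are tempting and not supported:

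- A reader might infer that all efficacy is tested by unadjusted bivariate comparisons. Motility capsule, CT and breath test results go into a repeated measures regression, and no method is fixed for the microbiota.
- A reader might infer that a false positive is almost certain: 1 − 0.95^47 = 91% for all 47 contrasts. That assumes tests at 0.05 and independence. The protocol states no alpha and makes no confirmatory efficacy claim; the primary endpoint is safety. With a correlation of 0.6 between endpoints the simulated figure is 53%. A multiplicity rule may sit in the analysis plan, and its absence here is not an error.

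**Conclusion.** The point holds for the 30 diary and questionnaire contrasts. As worded, the questionnaire comparison does not match hypothesis 3 and, taken literally, cannot answer it. The literal reading is open to placebo response, and to regression to the mean insofar as the eligibility score serves as the baseline score. If the sentence means change compared between arms, the analysis is valid but less precise than a baseline-adjusted one: about 10 percentage points of power at r = 0.5, 4 at r = 0.7 and 1 at r = 0.8.

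These sizes rest on assumed correlations, a 1 SD effect and 10 patients per arm. The gain is modest and shrinks as r rises. In a safety pilot this is a correction that should be made, not a flaw that undermines the trial.

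**What to change.** - State in the questionnaire sentence of section 2.4.2 that the comparison is FMT against placebo.
- For questionnaire and diary endpoints, estimate the arm difference with the baseline value as covariate (ANCOVA or an equivalent model) and report a 95% CI.
- Tie hypothesis 3 to the placebo-controlled first period and name one comparison for it. GSRS-IBS total at week 4 is one example; the choice of scale belongs to the investigators.
- Label the other symptom contrasts exploratory, and do not use within-arm change as evidence of superiority.
- Leave hypotheses 2 and 4 their own contrasts; the one named for hypothesis 3 does not answer them.

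The cost is one degree of freedom per model and changes of wording. No extra data, visits or patients are needed.

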## 2.5 Rationale

In patients with DM1 and severe gastrointestinal neuropathy, FMT could potentially change the composition of bacteria in the gut and reduce symptoms without the use of antibiotics. However, the use of FMT may have potentially serious side effects in patients with reduced gastric emptying, prolonged transit time through the small intestine, increased permeability of the gut and reduced resistance to infections. To date, no studies investigated the effects of FMT in patients with DM1 and severe gastrointestinal neuropathy. Therefore, it is necessary to evaluate the safety and pilot efficacy in a small group of patients before designing a large trial.

If this method is both acceptable, safe, and effective, it may provide a simple and antibioticfree way of treating gastrointestinal symptoms in DM1 in an out-patient setting. This study will provide data on safety, tolerability and pilot efficacy which is an absolute necessity for further research within the field.

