## 2.6 Background

### 2.6.1 Severe gastrointestinal neuropathy in diabetes mellitus

DM1 is strongly associated with diarrhea, nausea, vomiting, abdominal pain, bloating, constipation and faecal incontinence(1, 2). Though the severity of symptoms varies, severe cases suffer from daily uncontrollable diarrhea, vomiting, intense nausea, and faecal incontinence with severe consequences for social activities and quality of life(3). Additionally, nightly uncontrolled bowel movements pose a clinical challenge.

Earlier studies of patients with DM1 have demonstrated demyelination, axonal damage and reduced number of motor fibers in vagal nerves(4-6). Other studies report degeneration of nerve fibers within the enteric nervous system, including the Cajal cells (the pacemaker cell of the bowel)(7, 8). Today, it is assumed that diabetic gastrointestinal (GI) dysfunction is caused by autonomic neuropathy, dysfunction of the Cajal cells, and reduced contractility of the intestinal smooth muscle cells(7-9). The clinical effect of each component remains unknown.

### 2.6.2 Intestinal microbiota in diabetes mellitus type 1

Several studies have compared the gut microbiota of patients with early DM1 or even at a prediabetic stage with those of healthy volunteers. Findings have not been conclusive, but most have found reduced diversity of the intestinal bacterial community and increased proportion of *Bacteroides*(10). Preclinical studies support the hypothesis that specific features of the microbiota give rise to impaired intestinal permeability(11), which further influence T cell autoimmunity and B-lymphocytes.

This may lead to beta-cell destruction and DM1. However, most research on gut microbiota and DM has been in DM type 2. Thus, the impact of the microbiota in humans with DM1 and GI symptoms remains obscure

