FMT is a method used to induce permanent changes of the gut microbiota. The microbiota from minimally processed faeces, containing whole microbial communities from a healthy donor, is transferred to a recipient and drives a prompt engraftment of a donor-like microbiota in the recipient(15). FMT is an established and efficient treatment to recurrent infections with *Clostridioides difficile* infection (CDI) with cure rates above 90 %(16-19). Most of our knowledge about the safety of FMT relies on studies with patients with recurrent CDI, and these studies often include patients with a high age and comorbidity. Even in these patients, FMT is well tolerated(20).

The Center for Faecal Microbiota Transplantation (CEFTA) at AUH is among the foremost internationally within the clinical use of FMT(21, 22). Recently, we developed FMT capsules for oral intake. This application method is simple, with low risk and is able to induce longterm changes in the microbiota(23). In patients with DM1, this may potentially reduce diarrhea, bloating and pain, without massive use of antibiotics. Simple and appealing as it may seem, the use of FMT may have unwanted consequences in patients with DM1. Reduced gastric emptying, prolonged transit through the small intestine, increased permeability of the gut and reduced resistance to infections could potentially predispose to serious side effects of FMT.

To the best of our knowledge, no studies of FMT in patients with DM1 and severe bowel dysfunction have been performed. It would therefore be unethical to introduce treatment or to conduct large trials without first ensuring the safety and tolerability in a small group of patients. Furthermore, the design of a regular and sufficiently powered trial requires pilot data on the efficacy of treatment and information on whether a single dose is sufficient to cause changes in the gut microbiota. Based on the above considerations, we believe that FMT holds great promise in DM1 enteropathy, but a thorough study providing data on safety, tolerability and pilot efficacy is an absolute necessity for further research within the field.

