### 3.2.1.1 Clinical application of FMT

Clinical treatment takes place in the Department of Hepatology and Gastroenterology and will be administrated according to National clinical guidelines(24) and the described standard protocol (FMT ud-af-huset-vejledning, appendix 1). Prior to clinical treatment, the FMT is released and dispensed from the freezer of the CEFTA laboratory according to a standardised release protocol compliant with safety standards for handling blood components. Safety samples are taken from all FMT treatments, and the samples are saved for later traceability and testing.

All patients arrive fasting (6 hours) for their randomised dedicated treatment. Treatment with capsule-FMT or capsule-placebo takes place in outpatient observation rooms. Prior to treatment, patients receive a single dose of peristaltic 10 mg tablet metoclopramide. The physician responsible for the treatment breaks the seal and the capsules with FMT or placebo are indigested with diet soda over 10-30 minutes. Outpatients then leave the ward to their own home.

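### Hypothesis 2 expects a change in which bacteria are present, but no microbiota endpoint defined in the protocol measures one: flat alpha-diversity cannot separate no engraftment from engraftment at similar diversity

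*Protocol*

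**What the plan says.** Section 2.3.2, hypothesis 2: "Oral intake of FMT changes the microbiota of the colon and the effect lasts for at least 4 weeks".

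The protocol describes the expected effect in terms of composition. Section 2.5: "FMT could potentially change the composition of bacteria in the gut and reduce symptoms without the use of antibiotics". Section 2.6.4 says that transferred faeces "drives a prompt engraftment of a donor-like microbiota in the recipient". Section 2.6.3 names diversity and composition as two separate properties of the colonic microbiota.

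Section 2.4.2 introduces the microbiota endpoints with "Microbiota analysis on faecal samples collected at baseline and 4 weeks after each intervention period". It then lists endpoint 20, "Alpha-diversity of faecal microbiota, 16S", and endpoint 21, "Dysbiosis index". The protocol gives no definition or reference population for the index. No endpoint measures distance from baseline, similarity to the donor or the abundance of particular taxa. Sections 3.2.6 (Stool samples) and 7.1.2 mention microbiome or microbiota analysis but add no outcome.

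On what the pilot is for, Section 2.6.4 says that planning a powered trial needs to know whether one dose is enough to alter the gut microbiota. Section 3.1 adds that the design will allow the effect of FMT on the intestinal microbiota to be evaluated.

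**The concern.** The hypothesis and the endpoint that is meant to test it concern different properties. Turning the recipient's community into a donor-like one changes which bacteria are present. The usual alpha-diversity indices (richness, Shannon, Simpson) depend only on the set of abundances within one sample. Relabel every taxon and they do not move.

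If endpoint 20 showed no difference between FMT and placebo at 4 weeks, two readings would remain open: nothing engrafted, or a donor community of similar diversity took over. They point to different next trials. The first suggests revisiting how the treatment is delivered. The second says the microbiota did change and moves the question to symptoms. Endpoint 21 might settle the matter, but the protocol does not say what it is.

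**Working it through.** The protocol has no power calculation and no expected microbiota effect, so there is no stated figure to reproduce. What can be checked is how the metric behaves.

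**Inputs.** From the protocol: 20 patients (Section 4.1), taken as 10 per arm (1:1 assumed; Figure 1 shows 10). Samples are taken at baseline and 4 weeks after each intervention (Section 2.4.2), so the duration part of hypothesis 2 is covered. Assumed for illustration: 100 taxa, and the abundance patterns given below.

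**Formulas.** For relative abundances p (baseline) and q (week 4):
- Shannon: H = −Σ p·ln p
- Bray-Curtis distance: BC = 1 − Σ min(p, q)

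**Step 1: equal abundances, 100 taxa at 0.01 each.**
- Baseline: H = −100 × 0.01 × ln(0.01) = ln(100) = 4.61.
- All taxa replaced by 100 others: H = 4.61 (change 0); BC = 1 − 0 = 1.0.
- Half replaced: H = 4.61 (change 0); BC = 1 − 50 × 0.01 = 0.5.

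**Step 2: unequal abundances** (one random Dirichlet draw, parameter 0.3). Taxa are replaced by new ones at the same abundances.

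| Share of taxa replaced | Shannon before | Shannon after | Bray-Curtis from baseline |
|---|---|---|---|
| 25% | 3.467 | 3.467 | 0.304 |
| 50% | 3.467 | 3.467 | 0.619 |
| 75% | 3.467 | 3.467 | 0.674 |
| 100% | 3.467 | 3.467 | 1.000 |

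**Step 3: the favourable case for alpha-diversity.** Donor taxa are added alongside the residents, in the same community.

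| Donor share | Shannon | Bray-Curtis from baseline |
|---|---|---|
| 0% | 3.467 | 0.00 |
| 25% | 4.029 | 0.25 |
| 50% | 4.160 | 0.50 |
| 75% | 4.029 | 0.75 |
| 100% | 3.467 | 1.00 |

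The rise at 50:50 is ln 2 = 0.693, and 3.467 + 0.693 = 4.160. Alpha-diversity does respond to partial mixing, but not in step with engraftment: it rises and then returns to its starting value as replacement becomes complete.

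**Step 4: simulation at the trial's size.** 10 per arm, 2,000 runs, two-sided t-test at 0.05, random within-person drift in both arms, and taxa replaced at preserved abundances in the FMT arm only.

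| Share replaced | Shannon change significant | Bray-Curtis from baseline significant |
|---|---|---|
| 25% | 4.35% of runs | 100% |
| 50% | 4.65% | 100% |
| 90% | 4.30% | 100% |

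The Shannon column is about the false-positive rate. The contrast is this stark because the replacement taxa are wholly new and keep the old abundances. It shows that the failure can occur, not how often it would.

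**Step 5: scale.** With 10 per arm, the standardised difference detectable with 80% power is (1.960 + 0.842) × √(2/10) = 1.25 SD (normal approximation). Power at 0.5, 0.8 and 1.0 SD is about 20%, 43% and 61%. So even where alpha-diversity does move, a modest shift would usually be missed. This holds for any endpoint at this size, which favours one that responds directly to the expected effect.

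**The case against.** The strongest counter-arguments, and what stands of each:

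- **The dysbiosis index may do the job.** An index built as distance from a healthy reference responds to composition, and being a single score does not make it blind, since Bray-Curtis is also one number per patient. Its definition may be in the SAP, which is not at hand. This stands. A reader might infer that engraftment would produce a null result for hypothesis 2 as a whole; the protocol does not support that, because only endpoint 20 can be shown to miss replacement.
- **Alpha-diversity is a reasonable thing to measure.** Section 2.6.2 gives a ground: "Findings have not been conclusive, but most have found reduced diversity of the intestinal bacterial community and increased proportion of" *Bacteroides*. Step 3 shows that it can rise with partial engraftment. This stands. It would also be wrong to say that the endpoint presupposes low diversity at entry, since it can be measured at any starting level.
- **Hypothesis 2 speaks only of change, not of composition.** True of its wording, but Sections 2.5 and 2.6.4 say what change is expected, and Section 2.6.3 separates composition from diversity.
- **A rise in diversity could be due to diet or antibiotics.** A reader might add this as a further weakness. In the first four weeks it fails: the comparison is randomised and placebo-controlled (Sections 3.1 and 3.5), so an arm difference can be attributed to FMT. Only in the second period, when everyone receives FMT, is there no concurrent placebo.
- **This is SAP detail, and no data are lost.** Section 4.2 leaves the details of analysis to the SAP, which may choose an alpha index and define the dysbiosis index. That does not turn endpoint 20 into a measure of composition. The 16S data would indeed allow a distance analysis later, so the loss is of prespecification, not of information. A distance measure first chosen after unblinding would be post hoc.

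**Conclusion.** The concern holds in limited form. The protocol states a hypothesis about change in the colonic microbiota, describes that change as one of composition, and specifies for it one endpoint that does not register which taxa are present and one that it does not define. Flat alpha-diversity would leave no engraftment and engraftment at similar diversity indistinguishable.

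The size is illustrative: zero change in Shannon against a Bray-Curtis distance of 0.5 to 1.0 when half to all of 100 equally abundant taxa are replaced. This rests on replacement at matched abundances. With partial mixing, or with low diversity at baseline, alpha-diversity could well rise.

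The consequence is bounded: these are two of 22 secondary endpoints in a 20-patient pilot whose primary endpoint is safety. It still merits correction, because whether one dose changes the microbiota is something the pilot is expected to tell the next trial.

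A reader might also infer that a donor comparison is ready to run. Section 3.2.1.1 says "Safety samples are taken from all FMT treatments, and the samples are saved for later traceability and testing", but it does not mention research sequencing, so such use cannot be assumed.

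**What to change.** In Section 2.4.2, add as the main endpoint for hypothesis 2 the within-patient community distance (for example Bray-Curtis or UniFrac, from the planned 16S data) between the baseline sample and the sample 4 weeks after the first intervention, compared between FMT and placebo. Name one metric in advance. The placebo arm is essential here: a distance cannot be negative and will exceed zero from natural drift alone, so only the difference between arms is informative.

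Keep alpha-diversity and the dysbiosis index as supportive endpoints, and state or cross-refer to the definition of the index. Similarity to the patient's own donor batch is an optional addition, only if research use of the retained FMT samples is permitted; the main endpoint does not depend on it.

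Cost: one endpoint line and an analysis of data already planned, with no extra visits or patient samples. The optional donor part would add sequencing of stored samples. The change should be made before unblinding.
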